We will use paired-sample t-tests to account for the same participant providing both ratings on the adolescents and adults and to test whether there is a difference on the degree to which tobacco/nicotine, alcohol, cannabis, and illicit drug use is problematic. Given that the outcomes are rated on an ordinal scale, we will also perform a sensitivity analysis using the Wilcoxon Signed Rank test.

Exploratory Objective: Are there profiles of screening behaviors across the four substance categories?

To determine whether there are profiles among the screening behaviors across the four substance use categories, we will use hierarchical cluster analysis. We will choose the optimal linkage/method and similarity/distance measure based on the characteristics of the data. We will select the number of clusters based on the examination of the agglomeration schedule, selecting a range of solutions for further inspection based on the magnitude of dissimilar clusters being combined. We will then compare these profiles, both on the levels of screening behaviors that were inputs into the analysis as well as practitioner and practice characteristics that were external to the formation of the clusters. Selection of the final solution will be based on maintaining both interpretability and parsimony. This analysis will be performed separately for adolescents and adults.

Note that all analyses assume independence of observations by ignoring the clustering effect of providers nested within clinics. The degree to which any inferential analyses are

Document Owner: SUDS Study PI & Study Manager

valid will be dependent on the size of the intraclass correlation and the number of dentists that belong to the same clinic.

Missing Data. Data from incomplete questionnaires may be included in data analyses. Depending on the extent of missing data and available resources for analyses, the study team may consider statistically appropriate methods for imputing missing information. If the proportion of missing data is very small, we will rely on case-wise analysis.

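### The exploratory objective asks whether screening profiles exist, but the stated clustering procedure has no stated way to answer no, so a gradient of screening could be reported as distinct profiles

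*Protocol*

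**What the plan says.** The Exploratory Objective in Protocol Section 11.3 is an existence question: "Exploratory Objective: Are there profiles of screening behaviors across the four substance categories". The method is tied to that question: "To determine whether there are profiles among the screening behaviors across the four substance use categories, we will use hierarchical cluster analysis".

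The steps that follow are:

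- Linkage and distance: "We will choose the optimal linkage/method and similarity/distance measure based on the characteristics of the data".
- Number of clusters: "We will select the number of clusters based on the examination of the agglomeration schedule, selecting a range of solutions for further inspection". The range is guided by how dissimilar the clusters being merged are.
- Comparison: "We will then compare these profiles, both on the levels of screening behaviors that were inputs into the analysis". The same sentence adds a second comparison, on features of the dentist and the practice that played no part in building the clusters.
- Final choice: "Selection of the final solution will be based on maintaining both interpretability and parsimony".
- Scope: "This analysis will be performed separately for adolescents and adults".

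The section states no one-cluster outcome, no reference against which a jump in the schedule would be judged, and no stability check.

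**The concern.** Hierarchical clustering partitions any sample, whether or not groups exist. The rival explanation here is a continuum: some dentists screen more for everything, others less. The protocol treats that structure as plausible, since Section 11.3 considers reducing the items to component or factor scores for the first secondary objective. Yet the exploratory procedure moves from reading the schedule to comparing profiles without asking whether a single population would look the same.

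If it would, a smooth gradient may be cut into groups and published as types of dentist, once for adolescent and once for adult patients. The comparison on input items would appear to confirm this, although the clusters were formed to differ on exactly those items.

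**Working it through.** **Inputs.** From the protocol: n=825 (Section 11.2), four substance categories, hierarchical clustering, and a number of clusters read from the agglomeration schedule (Section 11.3). The protocol gives no figure for the cluster analysis. Its only precision figure for means at this n reproduces: 1.96/√825 = 0.068 SD. Assumed, because the protocol gives no values: one item per category and a common inter-item correlation ρ of 0, .3, .5 or .7.

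**Step 1: what the schedule shows when there are no profiles.** Each run draws 825 dentists from one multivariate normal population and applies Ward linkage (200 runs per ρ). Two quantities are recorded: the height of the last merge divided by the height of the one before, and the mean absolute difference between the two clusters per item.

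| ρ | Last/previous merge, median (5th-95th percentile) | Gap per item, simulated | Gap per item, formula |
|---|---|---|---|
| 0 | 1.13 (1.03-1.30) | 0.63 SD | not applicable |
| .3 | 1.69 (1.35-2.12) | 1.04 SD | 1.10 SD |
| .5 | 1.84 (1.41-2.29) | 1.25 SD | 1.26 SD |
| .7 | 1.84 (1.45-2.27) | 1.42 SD | 1.40 SD |

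A repeat of the simulation at ρ = .3 to .7 gave merge ratios of about 1.6 to 2.0 and gaps of about 1.0 to 1.4 SD. Neither quantity depends on a rule for choosing the number of clusters.

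**Step 2: check by formula.** Suppose the split falls at the median of the first principal component. The two halves of a standard normal differ in mean by 2√(2/π) = 1.596. With four equally correlated items, each item correlates √((1+3ρ)/4) with that component.

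- ρ = .3: 1.596 × √(1.9/4) = 1.596 × 0.689 = 1.10
- ρ = .5: 1.596 × √(2.5/4) = 1.596 × 0.791 = 1.26
- ρ = .7: 1.596 × √(3.1/4) = 1.596 × 0.880 = 1.40

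These agree with the simulated gaps. Differences of this size are what halving a gradient produces. At ρ = 0 the items share no dominant component, and the schedule shows little jump.

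**Step 3: do external characteristics settle it?** An external variable unrelated to screening differed between clusters (p<.05) in 2.5% to 7.5% of runs, so this comparison is not circular. An external variable correlated .2 with the general screening level, still with no profiles present, differed in 40% of runs at ρ = 0 and in 99% to 100% at ρ = .3 to .7. An external difference is therefore expected under a gradient too.

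**Step 4: can a rule that allows a negative answer work at this n?** The Ward two-cluster index (within-cluster over total sum of squares) was compared with 39 single-population datasets having the same covariance.

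- One homogeneous population: profiles wrongly declared in 1% (ρ = 0) and 3% (ρ = .5) of 100 runs each.
- Two real, equal-sized clusters: detected in 37.5%, 97.5% and 100% of 40 runs each at overall separations of 2, 3 and 4 SD. With four items, a separation of 2 SD is 2/√4 = 1 SD per item.

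The repeat gave a lower figure at 2 SD, so the range is about 27-38% there, and 90% or more at 3 SD or above.

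**The case against.** The strongest reply is that reading a schedule and choosing for interpretability are judgements. An analyst who saw no clear jump, or groups that made no sense, could report that no profiles emerged. That stands. A reader might infer that the procedure can never return a negative answer, but the text supports only that no way of doing so is stated. Coding the rule as a cut at the largest jump yields two or more clusters every time, but only because that coding excludes one cluster.

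A reader might also infer that the input-item comparison is a circular significance test. Section 11.3 names no test for it, although it names tests elsewhere, and Section 11.1 says formal hypothesis testing is not used to meet the study objectives. The comparison may be descriptive already. The choice of linkage and distance may likewise refer to the measurement scale of the items, which Section 3.1 says will vary, and not to tuning on results.

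A further reply is that cluster validation belongs in an analysis plan that is not shown. That would answer a silence. Here the protocol poses the existence question and writes out the rule meant to answer it, and that rule does not address it. Judgement does not rescue the rule either: with correlated items, the jump the analyst looks for is present without clusters.

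**Conclusion.** The point holds in limited form. The procedure has no stated route to a negative answer. With moderately correlated items and no profiles, it would present the analyst with a last merge about 1.6 to 2.0 times the previous one and clusters about 1.0 to 1.4 SD apart on every input. Neither stated comparison separates profiles from a gradient.

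These sizes rest on assumed values: four items, correlations of .3 to .7, normal data and Ward linkage. With uncorrelated items the jump largely disappears (ratio about 1.13).

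The reach is narrow. The objective is labelled exploratory, and no primary or secondary result depends on it. A reader might connect the profiles to the training and interventions mentioned in the Précis, but the Précis speaks of implementation gaps and their variation by practice and practitioner characteristics, and does not mention profiles.

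**What to change.** In Section 11.3, Exploratory Objective, add that:

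- One cluster is an admissible result. The chosen solution will be compared with single-population reference data matched on item margins and inter-item correlations (simulated reference or gap-type statistic), for adolescents and adults separately.
- Distinct profiles will be claimed only if the observed separation exceeds the reference. Otherwise the groups will be presented as descriptive segments of a continuum.
- Comparisons on the input items are descriptive only.

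The cost is a few sentences and a short simulation on data already collected, with no extra participants or items. The downside is limited sensitivity to weakly separated profiles (Step 4), so a negative result should be worded as no evidence of discrete profiles and not as proof of their absence. A different clustering model is not required. If only description is intended, rewording the objective to describe groupings would also remove the existence claim.

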12 SOURCE DOCUMENTS AND ACCESS TO SOURCE DATA/DOCUMENTS

Source data/documents will be maintained by the NCC for this study. The NCC will program the electronic questionnaire into their EDC. Participants will be sent an email invitation with a direct link to the electronic questionnaire. After completion of the electronic questionnaire, data will be available through the EDC.

Only study personnel (i.e. NCC, PI and designated study team members) will have access to the data. All research computers and associated study documents will be password-protected and maintained in compliance with ICH E6, Section 4.9 and regulatory and institutional requirements for the protection of confidentiality of subjects. Study staff will permit authorized representatives of NIDCR and regulatory agencies to examine (and when required by applicable law, to copy) research records for the purposes of quality assurance reviews, audits, and evaluation of the study safety, progress, and data validity.

The source documents for this study are:

- Electronic study questionnaire administered through the NCC EDC on the HUB website
- Selected data collected in the Network Enrollment Questionnaire

13 QUALITY CONTROL AND QUALITY ASSURANCE

For the Quality Control (QC) and Quality Assurance (QA) activities associated with data collection and processing, the NCC will develop a Data Management Plan in which the specific data QC/QA procedures will be provided. These procedures will include the development of automatic data quality checks in the EDC for the questionnaire and the processes related to data accuracy and completeness. The EDC will be programmed with edit checks and response limiters to reduce data response errors.

14 ETHICS/PROTECTION OF HUMAN SUBJECTS

14.1 Ethical Standard

The PI and Co-Investigators will ensure that this study is conducted in full conformity with the principles set forth in The Belmont Report: Ethical Principles and Guidelines for the Protection of Human Subjects of Research, as drafted by the US National Commission for the Protection of Human Subjects of Biomedical and Behavioral Research (April 18, 1979) and codified in 45 CFR Part 46 and/or the ICH E6.

14.2 Institutional Review Board

The protocol, informed consent form(s), recruitment materials and all participant materials will be submitted to the Network's Central Institutional Review Board (IRB) for review and approval. The UAB IRB for Human Use serves as the Network's Central IRB. Approval of both the protocol and the consent form(s) must be obtained before any participant is enrolled. Any amendment to the protocol will require review and approval by the IRB before the changes are implemented in the study.

For those study investigators requiring IRB approval by their institutions, the study institution PI will submit for IRB approval and provide the Central IRB with the appropriate approved IRB documents.

14.3 Informed Consent Process

The standard waiver of documentation of signed informed consent for internet-based surveys will be requested for this study. Consistent with regulations outlined by the Central IRB, informed consent language will be provided on the entry page to the questionnaire and will indicate that consent is provided if the respondent chooses to enter the questionnaire via the link they have been provided (tacit consent).

14.4 Exclusion of Women, Minorities, and Specific Age Groups

Network dentists of any age, sex/gender or racial/ethnic group may participate if they meet the eligibility criteria.

14.5 Participant Confidentiality

Participant confidentiality is strictly held in trust by the investigators, study staff, and the study sponsor and their agents. The study protocol, documentation, data, and all other information generated will be held in strict confidence. No information concerning the study, or the data will be released to any unauthorized third party without prior written approval of the study sponsor.

Practitioners' pre-assigned identification numbers (PIDs) (practitioner IDs assigned by the Network) will be used to maintain study records and organize data files. A file linking participants' names with their unique identification number will be kept in a password-protected file by the NCC.

The study monitor or other authorized representatives of the NIDCR may inspect all study documents and records required to be maintained by the investigator.

The National Program Manager, who will be responsible for ensuring Network dentists completing the questionnaire are remunerated \$50, will be provided the minimum information necessary from the questionnaire to fulfill the responsibility of appropriately directing practitioner payments to their desired address.

Certificate of Confidentiality

To further protect the privacy of study participants, the Secretary, Health and Human Services (HHS), has issued a Certificate of Confidentiality (CoC) to all researchers engaged in biomedical, behavioral, clinical, or other human subjects research funded wholly or in part by the federal government. Recipients of NIH funding for human subjects research are required to protect identifiable research information from forced disclosure per the terms of the NIH Policy (https://humansubjects.nih.gov/coc/index). As set forth in 45 CFR Part 75.303(a) and NIHGPS Chapter 8.3, recipients conducting NIH-supported research covered by this Policy are required to establish and maintain effective internal controls (e.g., policies and procedures) that provide reasonable assurance that the award is managed in compliance with Federal statutes, regulations, and the terms and conditions of award. It is the NIH policy that investigators and others who have access to research records will not disclose identifying information except when the participant consents or in certain instances when federal, state, or local law or regulation requires disclosure. NIH expects investigators to inform research participants of the protections and the limits to protections provided by a Certificate issued by this Policy.

Confidentiality of Data Sharing

As described in section 16, it is NIH policy that the results and accomplishments of the activities that it funds should be made available to the public (see https://grants.nih.gov/policy/sharing.htm). PIs and funding recipient institutions will ensure that all mechanisms used to share data include proper plans and safeguards to protect the rights and privacy of individuals who participate in NIH-sponsored research.

15 DATA HANDLING AND RECORD KEEPING

The study team is responsible for ensuring the accuracy and completeness of the data reported, and for following the data collection procedures as outlined in the DMP. Access to study data will be provided to study team members by NCC staff.

15.1 Data Management Responsibilities

The PI will work closely with the NCC to ensure that the electronic surveys are collected appropriately and completely, and that confidentiality is being maintained according to protocol-specified procedures. Conference calls will be held approximately twice per month during the data collection phase to monitor progress, manage study documentation and procedures, and troubleshoot any problems.

The NCC will develop and maintain an EDC system including the study questionnaire. The DMP will include details on the EDC and procedures that will be followed to launch and monitor the study. The data reported in the Network's Practitioner Database will be used by the NCC to identify eligible dentists for this study.

15.2 Data Capture Methods

Data from the electronic questionnaire will be captured using forms in the EDC. The NCC will conduct preliminary testing and review of data fields in the initial programming and online launch of the questionnaire. The NCC will ensure that all required data are collected per protocol requirements and edit checks will be programmed in the web questionnaire to correct data issues in real time. The study team will ensure that data fields in the system are checked for completeness and accuracy so data entered in the EDC can be validated and data errors corrected in real time. Reports or tools will be developed to help monitor the data capture activities. The reports with the summary of data completeness and accuracy will be made available to the study team and NIDCR as requested.

15.3 Schedule and Content of Reports

Ongoing reports to monitor enrollment will be produced approximately monthly, or more frequently if desired, for study team and NIDCR review. The contents of the reports will include the summary of data collected and can be developed in separate sections by key characteristics or regions.

Final data analysis reports that address objectives of the study will be produced by the NCC for review by the study team and NIDCR. The content of these reports will be determined by the study team and the NCC and defined in the Statistical Analysis Standard Operating Procedure.

The procedure for locking the database prior to final analysis will be detailed in the study Data Management Plan. Briefly, the EDC data will be locked, and final study datasets will be generated at the end of the study. Prior to locking the database, the NCC's Data Manager (DM) or designee will ensure all data are complete and clean as determined by

the study team. Then, the DM will obtain approval from the PI to proceed with the data lock.

No masking or coding is anticipated for this study.

15.4 Study Records Retention

Study records will be maintained for at least three years from the date that the grant federal financial report (FFR) is submitted to the NIH or longer as dictated by local IRB or state laws/regulations.

As outlined by IRB regulations, data will be destroyed in an appropriate and safe way. The file connecting subjects' names with their unique identification number will be kept in a password-protected file by the NCC and PI, in accordance with IRB regulations, before being securely erased on agreement by the ARC Director, the NCC Director and the PI.

15.5 Protocol Deviations

A protocol deviation (PD) is any change, divergence, or departure from the study procedures described in the IRB-approved clinical study protocol. The deviation may be on the part of the participant, the investigator, or study staff.

Consistent with the investigator obligations in the ICH E6 Guideline for Good Clinical Practice, the PI will document in study source documents and explain any deviation from the IRB-approved protocol. The PI will report to the IRB any deviations or changes made to eliminate immediate hazards to participants and any changes that increase risk to participants and/or significantly affect the conduct of the study.

Protocol deviations will be assessed for their impact on safety, study operations, and data integrity. Appropriate corrective and preventive actions will be implemented if warranted.

16 PUBLICATION/DATA SHARING POLICY

This study will comply with all applicable NIH Data Sharing Policies. See https://grants.nih.gov/policy/sharing.htm for policies and resources.

NIH Public Access Policy

The NIH *Public Access Policy* requires scientists to submit final peer-reviewed journal manuscripts that arise from NIH funds to *PubMed Central* immediately upon acceptance for publication. This ensures that the public has access to the published results of NIH funded research.

The Network's "National Dental PBRN Publications, and Presentations Policy" document is available at the network's public web site at https://www.nationaldentalpbrn.org/publications/.

